To evaluate a randomized control trial (RCT) of RVA Breathes.

- Conditions will be compared on the primary outcome of healthcare utilization (e.g., a composite of the frequency of asthma-specific ED visits and hospital admissions).
- Conditions will be compared on the secondary outcomes of school absences and medication usage.
- We hypothesize that children in the two active interventions will achieve greater reductions in healthcare utilization and school absences, and increases in controller medication usage at post-treatment and follow-up than children in the comparator condition.
- We will also *explore* differences in outcomes between the two active intervention conditions. This will provide important data for determining best practices in subsequent iterations of RVA Breathes.

C2 Secondary Aims

a) To evaluate the effectiveness of the RCT on secondary outcomes including asthma control, symptoms, and quality of life (QOL).

- We hypothesize that secondary outcomes of children in the intervention groups will be superior to those of the control group.

b) To identify putative mediators and moderators (e.g., caregiver asthma self-management skills, perceived stress, and depressive symptoms) of treatment outcomes.

- We hypothesize that intervention effects will be mitigated in families with caregivers with lower levels of asthma self-management skills at baseline, as well as in those with higher baseline levels of stress and depressive symptoms.

C3 Rationale for the Selection of Outcome Measures

[figure not shown]
Outcome measures were informed by the Social-Ecological Model and Interactive Systems Framework and drawn from recommendations by the Asthma Outcomes Steering Committee.

C4 Rationale and Risk/Benefits

Given that pediatric asthma disparities are a serious public health problem, the significance of this research project is high. As the study risks are small, the benefit to society outweighs subject risk. New information learned from this intervention study has the potential to improve the health and lives of urban children with asthma, as well as their families.

D Study Design

D1 Overview of Study Design

D2 Subject Selection and Withdraw

2.a Inclusion Criteria

Children and their caregivers must meet all of the inclusion criteria in order to be eligible to participate in the study:

- Child between the ages of 5 and 11
- Physician diagnosed asthma in child

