 - Caregivers will complete the Pediatric Asthma Caregiver Quality of Life Questionnaire (PACQLQ) and report on their own quality of life.
 - Caregivers will complete the Asthma Self-Efficacy Management Questionnaire (ASMQ), Perceived Stress Scale (PSS), Centers for Epidemiologic Studies Depression Scale (CES-D), and Stressful Life Events and Conditions Checklist (SLECC).

Changes due to COVID-19:

- Baseline sessions occur over the phone or via video (see Section E3)
- Verbal consent is obtained with documentation (see Section D2, 2.d.i.)
- Question added to packet:
 - "How has COVID-19 impacted your family?," "How has COVID-19 impacted your child's asthma care?," "What has it been like not being able to access your child's school nurse for asthma care?"
- Payment occurs via contactless payment drop-off (see Section E3)

E5 Session 1, Month 1

Within 2 weeks after the baseline session, families in the two active intervention arms will complete the first of 4 sessions. For children in the CHW + Healthy Homes + school intervention arm and children in the CHW + Healthy Homes intervention arm, this will be the first home visit that includes both family-based asthma education and a home assessment by Healthy Homes. Home visits will last 2-2.5 hours, and include both the CHW and a representative from Healthy Homes.

After the first visit, CHWs in consultation with the care management committee, will update providers with a summary of information covered at the session. Data from family interactions with the PCP will be communicated back to CHWs.

For children in the CHW + Healthy Homes + school intervention arm, CHWs will begin the process of communicating with the schools to ensure that children have the necessary forms and medication in place. Caregivers will complete a release to allow us to contact school nurses and the child's PCP and/or asthma provider. School nurses and PCPs will be alerted to the child's participation in an active arm of RVA Breathes. School nurses will follow the standardized protocol in their interactions with the student; interactions will be documented and relayed to CHWs.

For children in the E-SOC group the project coordinator will mail the first set of publicly available information on asthma.

Intervention Session 1:

- CHW and Healthy Homes assessor describe program aims for the year. Work with parent and child to outline their goals for the year as an RVA Breathes participant.

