Aim 1: We hypothesize that children in the two active interventions will achieve reductions in healthcare utilization (e.g., asthma-specific ED visits, hospital admissions) and school absences, and an increase in controller medication use (calculated from refill data from insurers) at post-treatment and follow-up than children in the comparator condition. Our primary outcome, healthcare utilization, will be defined as a composite of the frequency of asthma-related inpatient and ED visits. A composite variable (i.e., sum score) that takes into account the frequency of asthma-related inpatient and frequency of ED visits will be calculated for each participant. At baseline, historical data will be obtained to ensure that we have captured utilization for the 9 months prior to the baseline visit (i.e., utilization before the intervention begins). Our primary endpoint is the change in mean rate of ED/hospitalization in 9 months before to 9 months after RVA Breathes across groups. Generalized Linear Mixed Models (GLMM) will be used to determine within person changes in healthcare utilization across time, and then differences in healthcare utilization between groups (e.g., intervention vs. control). Thus, our main outcome is change in healthcare utilization at the individual level as an average of individuals. We will also *explore* differences in outcomes between the two active intervention conditions [(1) asthma education + home remediation + school intervention vs. 2) asthma education + home remediation] to determine the value of adding a school-based component. Differences in healthcare utilization (and other outcomes) will again be tested using a Generalized Linear Mixed Model (GLMM). GLMM models will be fit to multiple types of dependent variables including, Gaussian/Normal, Binomial, Poisson and Negative Binomial. The GLMM model fit will include a between-subject factor (Group, representing the control group and the two intervention groups) and will also include a random effect for the cluster (school). These models will be modified in longitudinal assessments by the inclusion of a within-subject factor (Time [pre, post]) and the interaction between Group and Time variables. The inclusion of the interaction terms allows for a formal test of differing courses between the groups over time. To account for seasonality and the impact of COVID-19, we will include sine and cosine functions of $x = 2\pi \cdot (\text{time} / \text{max(time)})$ covariates and COVID-19 impact as covariate in analyses. COVID-19 impact will be designated as March 13, 2020 and Covariate=0 for months before COVID-19 and Covariate=1 for months after COVID-19. We will adjust for multiple comparisons using the Holm-Bonferroni method. In addition to healthcare utilization, we will also consider changes in the secondary outcomes of asthma action plans and controller medication use between conditions.

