
Aim 2: We hypothesize that secondary outcomes (asthma control, symptoms, quality of life) of children in the intervention groups will be superior to those of the control group. These outcomes will be tested using the GLMMs described under Aim 1 utilizing the proper distribution and link functions for the outcome variable examined.

Aim 3: We hypothesize that intervention effects will be mitigated in families with caregivers with lower levels of asthma self-management skills at baseline, as well as in those with higher baseline levels of stress and depressive symptoms. These outcomes will also be tested using the GLMMs described under Aim 1 utilizing the proper distribution and link functions for the outcome variable examined that have been modified by the inclusion of an additional effects measuring caregivers' self-management skills, as well as stress and depressive symptoms. The inclusion of these covariates will allow us to adjust the intervention effects and increase the

generalizability of the intervention effects based upon caregivers' characteristics.

Sample size. From RVA Breathes baseline data, Group 1 children (full intervention: CHW + HH assessors + school) had a 9-month ED visit rate of 2.22 visits. Group 2 (CHW + HH, no school) had a 9-month ED rate of 1.89 visits, and Group 3 (control) had a 9-month ED rate of 1.68. We used recent published rates from a comparable study that considered changes in child asthma-related ED visits from 6 months prior to intervention to 6 months post-intervention (Johnston et al., 2019). In this study, the intervention group went from 2.0/6mo (pre) to 0.55/6mo (post) and the control group went from 1.3/6mo (pre) to 0.85/6mo (post). Thus, the intervention group had a 72% reduction $((2.0-0.55)/2.0 = 0.72)$ and the "control" group had a 35% reduction $((1.3-.85)/1.3 = 0.35)$.

Basing our numbers on these same rates, we would expect the following power estimates with 9-month follow up data: 14% for Groups 1 vs. 2, 97% for Groups 1 vs. 3, and 88% for Groups 2 vs. 3. Using alpha = .0167, we would assume average clusters of 10 in 24 schools for 240 enrolled participants. Allowing for 20% attrition, this would be 300 participants. Moreover, using a Poisson model for analyses, we would use a CVB (between-cluster coefficient of variation) instead of ICC. These analyses would use a CVB for G1 vs. G2 = 0.1331, for G1 vs. G3 = 0.1820, and for G2 vs. G3 = 0.0502.

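### SAP Aim 3 adds the caregiver variables only as covariates, so its model has no term that tests whether the intervention effect is weaker in some families

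*SAP*

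**What the plan says.** The hypothesis in SAP Aim 3 is that "intervention effects will be mitigated in families with caregivers with lower levels of asthma self-management skills at baseline", and likewise in families where baseline stress or depressive symptoms are higher. Protocol C2 (Secondary Aims, item b) states the same hypothesis under an aim that begins "To identify putative mediators and moderators".

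For the analysis, Aim 3 refers back to the Aim 1 GLMMs, "modified by the inclusion of an additional effects measuring caregivers' self-management skills, as well as stress and depressive symptoms". The next sentence gives the purpose of the added terms: "The inclusion of these covariates will allow us to adjust the intervention effects". It goes on to claim that this makes the effects more generalizable.

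The Aim 1 model has Group (control and two intervention arms), Time (pre, post), "the interaction between Group and Time variables", seasonality terms, a COVID-19 covariate and a random school effect. Of the Group x Time term the SAP says: "The inclusion of the interaction terms allows for a formal test of differing courses between the groups over time". Neither document names a product of a caregiver variable with Group, or with Group x Time.

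**The concern.** A claim that an effect is weaker in some families is a claim about an interaction. Entering a baseline variable as a covariate answers a different question: whether that variable predicts the outcome. Self-management skills, stress and depressive symptoms may well predict asthma outcomes whatever the arm. A significant coefficient is therefore quite possible without any moderation, and could be reported as support for Aim 3.

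Followed as written, the plan would report an adjusted average effect and some prognostic coefficients. A stated secondary hypothesis would stay untested although the data to test it are collected. Covariate adjustment also does not by itself make an average effect more generalizable.

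**Working it through.** The SAP gives no sample size, power or alpha for Aim 3, so there is no figure to reproduce. The check is of model terms, followed by a note on how precise the missing term would be.

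**Terms.** Let M be a baseline caregiver variable. On the link scale the stated Aim 3 model is

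Group + Time + Group x Time + M + seasonality + COVID-19 + random school.

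For intervention arm k, the effect (difference in pre-to-post change from control) is the Group x Time coefficient b_k. It does not contain M, so it is the same in every family. The hypothesis needs an effect of the form b_k + d_k x M, and d_k is the coefficient of Group x Time x M. With two intervention arms there are 2 such coefficients per moderator, and 3 x 2 = 6 for the ASMQ, PSS and CES-D per outcome. The SAP specifies 0.

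**What the covariate coefficient responds to.** This was simulated with 240 children, 24 schools, the SAP's rates and 400 runs per setting. The moderator effects are assumed and are not in the documents.

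| Setting | Covariate term significant at 5% |
|---|---|
| Prognostic (log rate ratio 0.2 per SD), no moderation | about 99.8% |
| True moderation (0.3 per SD on the intervention-arm change), not prognostic | about 19% |

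The coefficient follows prognosis. The simulation is only illustrative: it had no child random effect, and its interaction test was somewhat liberal (8 to 10% at a nominal 5%).

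**Precision if the term is added (Group 1 versus Group 3, utilization).**

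Inputs from the SAP sample size section:
- 240 children in 24 schools, taken here as 80 children and 8 schools per arm.
- 9-month pre rates of 2.22 and 1.68. These are ED visits only, whereas the outcome also counts inpatient visits.
- Reductions of 72% and 35%, giving post rates 2.22 x 0.28 = 0.622 and 1.68 x 0.65 = 1.092.
- Between-cluster coefficient of variation 0.182.

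Assumptions: Poisson variance, and independent pre and post counts.

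- Group x Time: V = (1/2.22 + 1/0.622 + 1/1.68 + 1/1.092)/80 = 0.0446, so SE = 0.211.
- Between-school part: 2 x 0.182²/8 = 0.0083. Including it, V = 0.0529 and SE = 0.230.
- Continuous moderator, per SD: SE about sqrt(0.0446) = 0.21.
- Moderator split 50/50: sqrt(4 x 0.0446) = 0.42 if it varies within schools, so that the school part cancels; sqrt(4 x 0.0529) = 0.46 if it does not vary within schools.
- Variance twice the mean (assumed): multiply by 1.414, giving 0.30 per SD and 0.60 for the split.
- 95% interval, factor either side of the per-SD estimate: exp(1.96 x 0.211) = 1.5 to exp(1.96 x 0.299) = 1.8.
- Per-SD ratio detectable with 80% power at two-sided 0.05: exp(2.80 x 0.211) = 1.8 to exp(2.80 x 0.299) = 2.3.

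A separate simulation with no true moderation (800 replicates per setting) gave empirical SDs of 0.22 and 0.30 for the continuous moderator, and 0.43 and 0.62 for the split.

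**The case against.** The strongest reply is that Aim 3 is loosely worded rather than wrong. In mixed-model usage, added effects can include interactions. Aim 1 uses a similar construction when it adds Time together with its interaction with Group. The Aim 3 sentence on generalizability also ends by tying the effects to caregiver characteristics, which could hint at effects that depend on them. An interaction may have been intended.

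That possibility stands, but it does not rescue the text. The SAP itself calls the added terms covariates for adjustment, and Aim 1 shows that the authors name an interaction when they want one. If one was intended, its form, the contrast and the handling of multiplicity are still undefined.

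Two further points are fair. First, the precision figures describe the remedy and do not measure the defect, which is simply that the term is absent. They also depend on the contrast. Pooling the intervention arms (mean pre rate 2.055, post 2.055 x 0.28 = 0.575, 160 children) against control gives V = (1/2.055 + 1/0.575)/160 + (1/1.68 + 1/1.092)/80 = 0.0328. The SE is then about 0.18, and the detectable ratio about 1.7 to 2.0.

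Second, the gain is limited. The SAP's assumed main effect is a ratio of 0.65/0.28 = 2.32, so with doubled variance the detectable Group 1 versus 3 interaction per SD is about as large as that whole effect. This argues for interval estimates over reliance on a test. It does not argue for leaving the term out.

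**Conclusion.** The concern holds. The Aim 3 model as written has no coefficient that can test the Aim 3 hypothesis: 0 interaction terms where three groups and three moderators call for 6 per outcome, or 3 if the intervention arms are pooled. This follows from the terms the SAP lists and needs no numerical assumption.

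The precision figures (SE per SD about 0.21 to 0.30, detectable ratio about 1.8 to 2.3 for Group 1 versus 3) do rest on assumptions: 80 children per arm, the SAP's ED rates and reductions, independent pre and post counts, and variance between one and two times the mean. They show only that the added estimates will be imprecise.

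The consequence is confined to a secondary aim. It should be fixed.

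**What to change.** - For each of the baseline ASMQ, PSS and CES-D, kept continuous, add to the Aim 1 model the moderator, its products with Group and with Time, and Group x Time x moderator. If the model is instead one of the post-treatment outcome adjusted for baseline, Group x moderator is enough.
- Test that interaction, and report the intervention effect with confidence intervals across the moderator range.
- State which outcomes it covers, whether the contrast is each intervention arm or both pooled against control, whether moderators enter singly or jointly, and whether Holm-Bonferroni applies.
- Label the analysis secondary with low precision. If outcome data have already been seen, say that the interaction was specified afterwards.
- Delete the statement that covariate adjustment increases generalizability.
- A separate and lesser point: Protocol C2 also promises mediators, but the SAP has no mediation analysis. Either specify one using the post-intervention measures (Protocol E10) or drop mediators from the aim.

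The cost is SAP wording and a few model terms. The three scales are already completed at baseline (Protocol E4), so no new data are needed. The price is wide intervals on the interactions.

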2.d.i. Changes to recruitment and consent process due to COVID-19: Recruitment in the community will be limited to remote options (e.g., as a part of virtual newsletters or emailed flyers). School nurses will still call potentially eligible families, we will still receive lists of children seen at VCU and BSHS, and letters will be mailed from provider offices. Families will be screened using our IRB approved screening materials. If a family screens eligible, the caregiver will be told that, "Due to COVID-19 and recommendations from the Health Department, and for the safety of families and our staff, we are now conducting RVA Breathes remotely. This means that the consent process and all research and intervention sessions will be conducted over the phone or video." A phone or video session will then be scheduled to conduct the verbal consent process and complete baseline measures. Questions will be asked to the parent and then to the child separately. If the child is not available or is not comfortable answering questions, these will be marked as missing data. IRB has approved a waiver of documentation of consent for parents in RVA Breathes. This is for their participation in the study and for the participation of their child. We will instead obtain verbal consent and will document in our research record using a consent documentation form that records that consent was given, what day/time it was given, and who was present for the discussion. We are also approved to waive child assent, which is recorded on the consent documentation form.

2.e Randomization Method and Blinding

Families will be randomized at the school level. In consultation with RPS, we will match elementary schools based on demographics and location, and whether school nurses travel among schools; 8-9 schools will be included in each condition. We will use a block randomization scheme. After the baseline session is complete, the project coordinator will randomize the family to one of the 3 conditions based on the child's school. Given the nature of our program, it will not be possible to blind participants or study staff to their condition. Analysts collecting data from insurance companies will be blind to condition.

2.f Risks and Benefits

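### With about 24 randomised schools, the SAP names no small-sample test and no school-by-time effect, so the error rate of the primary Group x Time test is not secured

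*SAP*

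**What the plan says.** Protocol section 2.e (Randomization Method and Blinding) makes the school the unit of allocation: "Families will be randomized at the school level", and "8-9 schools will be included in each condition". It also says that "we will match elementary schools based on demographics and location, and whether school nurses travel among schools", and that a block scheme will be used. It does not give the size of the matched sets or blocks.

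The SAP's sample size text sets alpha at .0167 and assumes "average clusters of 10 in 24 schools for 240 enrolled participants". It gives between-cluster coefficients of variation (CVB) of .1331, .1820 and .0502 for the three pairwise comparisons.

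Under Aim 1 of the SAP, the model for every outcome is a GLMM that "will also include a random effect for the cluster (school". For longitudinal outcomes it adds Time (pre, post) and Group x Time: "The inclusion of the interaction terms allows for a formal test of differing courses between the groups over time". On multiplicity: "We will adjust for multiple comparisons using the Holm-Bonferroni method". The primary endpoint is the change in the ED/hospitalisation rate from 9 months before to 9 months after the programme.

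Neither document names a reference distribution, denominator degrees of freedom, a permutation test or a cluster-summary test. Neither commits to large-sample z or chi-square tests. The model has no school-by-time effect and no term for the matched sets or blocks.

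**The concern.** Each pairwise comparison rests on 16 to 18 schools, and the whole trial on 24 to 27. With so few units, two separate things can make the nominal .0167 wrong.

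- **Reference distribution.** Between-school variance is estimated from few schools. A statistic built on it follows a t distribution more closely than a normal one.
- **Variance structure.** The primary test compares change over time. A school random intercept shifts a school's pre and post rates alike, so it does not describe schools that change by different amounts. If they do, the model-based standard error of Group x Time is too small.

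Holm-Bonferroni orders the p-values it is given and cannot repair either fault. The SAP is also silent on the test itself. A z test and a t test on school-based degrees of freedom would both comply with it, and a statistic between about 2.4 and 2.7 would be significant under one and not the other.

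**Working it through.** **Inputs.** From the SAP: alpha .0167, 24 schools, 10 children per school, the CVBs, baseline 9-month ED rates of 2.22 (Group 1) and 1.68 (Group 3), reductions of 72% and 35%, and 20% attrition. From Protocol 2.e: 8-9 schools per arm. Assumed: two-sided tests (the SAP does not say), equal school sizes, and gamma-distributed school effects.

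**1. The plan's own figures.** .05/3 = .0167; 24 x 10 = 240; 240/(1 - .20) = 300. All three reproduce.

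**2. School-level contrast judged against the normal.** The two-sided normal critical value for .0167 is 2.393. True error = 2 x P(t_df > 2.393).

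| Basis | df | True error | Ratio to .0167 | Correct t critical value |
|---|---|---|---|---|
| Two arms of 8 (16 - 2) | 14 | .0313 | 1.87 | 2.717 |
| Two arms of 9 (18 - 2) | 16 | .0293 | 1.76 | 2.672 |
| Three arms, 24 schools (24 - 3) | 21 | .0261 | 1.56 | 2.600 |
| Three arms, 27 schools (27 - 3) | 24 | .0249 | 1.49 | 2.573 |

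At nominal .05, the last Holm step, the same calculation gives .063 (21 df) to .070 (14 df).

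**3. Poisson GLMM, post-period difference, Wald z** (simulated; rate 0.8 per child assumed). Rejection under the null was .013-.014 at CVB .0502, .019-.020 at .1331 and .022-.023 at .1820, or roughly 0.8 to 1.4 times nominal. With child-level overdispersion left in a Poisson model (squared CV of 1, assumed) it was .031-.041.

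**4. Group x Time, the primary contrast** (simulated; 8 v 8 schools of 10, rates 1.9 pre and 0.9 post assumed). The statistic is the difference between arms in log(post total/pre total). Its standard error under a school intercept alone is sqrt(1/A + 1/B + 1/C + 1/D), where A to D are the four event totals.

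| School-by-time CV (assumed) | Rejection with z at nominal .0167 |
|---|---|
| 0 | .016-.018 |
| .133 | .021-.025 |
| .182 | .028-.031 |
| .30 | .051-.057 |

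With no school-by-time variation, raising the school-intercept CV to .5 left the rate at about .017, which confirms that the intercept cancels.

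**5. Does a t cut-off alone repair it?** No. Applied to the same intercept-only statistic, the 14 df cut-off rejected about .006 with no school-by-time variation (too strict) and about .03 at CV .30 (too loose). With period-specific child overdispersion (squared CV of 1, assumed) left in a Poisson model, z rejected .106 and the t cut-off .064. A t test on school-level changes, or a permutation within sets, stayed at about .011 to .019 in every setting run.

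**6. Cost in power, Group 1 v Group 3, change scale, 8 schools per arm.** Post rates are 2.22 x .28 = .622 and 1.68 x .65 = 1.092. The changes are 1.598 and .588, a difference of 1.010. Variance per school pair = (2.22 + .622 + 1.68 + 1.092)/10 + .182^2 x (1.598^2 + .588^2) = .561 + .096 = .657. The standard error is sqrt(.657/8) = .287, and the ratio 3.52. Power is 87% with the normal cut-off, and from the noncentral t 78% on 14 df and 81% on 21 df. This does not reproduce the SAP's 97%, whose formula is not given; it serves only to price the change of cut-off.

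**The case against.** The strongest reply is that the SAP does not choose a z test. Silence on degrees of freedom is not a decision to ignore them, and standard software offers t and F tests for such models. This stands: the error rates above are a risk of the omission, not a stated property of the plan.

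The second reply is that the primary contrast is within school. A school intercept cancels, and at the SAP's CVBs a z test of Group x Time is then at its nominal level; a t cut-off would only make it needlessly strict. This also stands, but only if schools do not differ in change. The seasonal and COVID-19 covariates may absorb some of such differences. They cannot absorb what is specific to a school, such as nursing cover.

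A reader might infer that the plan nearly doubles its alpha. The documents do not support that. The factor of 1.87 belongs to a two-arm, school-level contrast on 14 df with a normal reference. It is 1.5 to 1.6 for the three-arm model, and 0.8 to 1.4 for a Poisson GLMM of post-period rates at the SAP's own CVBs. A reader might also infer that the error favours a finding of benefit. It does not: a standard error that is too small in a two-sided test raises false findings of harm and of benefit alike.

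**Conclusion.** The omission is real and should be corrected. Its size depends on a quantity the documents do not give.

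- For a school-level contrast with a normal reference, the true error at nominal .0167 is about .025 to .031.
- For the primary Group x Time contrast with a school intercept only, it is about nominal with no school-by-time variation, about .02 to .03 if that variation has a CV of .133 to .182, and about .05 at .30.

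The SAP's CVBs are given for its power calculation, not as school-by-time values. Using .133 and .182 as such is an assumption, and .30 is purely illustrative. The results also rest on two-sided tests, equal school sizes and the assumed rates.

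This is more than a missing detail of wording, because no choice of cut-off on the intercept-only model holds the error rate across these settings, whereas school-level testing does.

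**What to change.** Before the group comparisons are run, amend the SAP's Aim 1 text to:

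1. Add a school-by-time random effect to the Group x Time model, and state how overdispersion is handled (for example, negative binomial, which the SAP already lists).
2. Test all Group and Group x Time effects with t or F statistics on school-based degrees of freedom (schools minus arms: 21 to 24 for 24 to 27 schools). Keep these degrees of freedom if the school-by-time variance is estimated as zero.
3. Confirm the primary contrasts with a permutation test that re-allocates schools within the matched sets or blocks actually used, and state the size of those sets.
4. State whether tests are one- or two-sided.

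The work is SAP wording and standard software. The statistical cost is real:

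- Critical values rise from 2.39 to about 2.57-2.72, so intervals based on the same standard error widen by about 7% to 14% (2.573/2.393 = 1.075; 2.717/2.393 = 1.135).
- Power for Group 1 v Group 3 falls from about 87% to 78-81% on the one change-scale calculation above.
- Permutation p-values may be coarse. If the sets were 8 triplets (an assumption), a pairwise test has 2^8 = 256 allocations and two-sided p-values of 2/256 = .0078, 4/256 = .0156 and 6/256 = .0234, so only two attainable values fall below .0167. The permutation test is therefore better as confirmation than as the sole primary test.

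### The SAP's power figures use three unexplained between-school CVBs for the same 24 schools; they conflict under ordinary variance pooling, and the stated powers need restating from one value and one formula

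*SAP*

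**What the plan says.** The SAP's Sample size section plans on a Poisson model with schools as clusters, 24 schools averaging 10 children. It gives power as "14% for Groups 1 vs. 2, 97% for Groups 1 vs. 3, and 88% for Groups 2 vs. 3", at "Using alpha = .0167". It then lists the between-school variation assumed: "These analyses would use a CVB for G1 vs. G2 = 0.1331, for G1 vs. G3 = 0.1820, and for G2 vs. G3 = 0.0502". It does not say which data these came from, how the two arms of a pair were combined, or why a school-level quantity changes with the contrast. It gives no range of alternatives.

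Two other places bear on this. Under Aim 1 the SAP says that the analysis model "will also include a random effect for the cluster (school") and describes no school variance specific to a pair of arms. Protocol section D2, 2.e says "8-9 schools will be included in each condition".

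**The concern.** Each arm's schools enter two of the three contrasts, so the three CVBs are not free of one another. With near-equal numbers of schools per arm, a pair's squared CVB should lie close to the average of its two arms' squares, and the printed values do not fit that. A model with one school random effect would in any case suggest one CVB throughout.

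Group 2 against control is part of the primary hypothesis, and its 88% was computed with the smallest of the three values: 0.0502 squared is 0.0025, against 0.0331 for the contrast that shares its control schools. If that power is too high, a null result for Group 2 would be read as coming from a stronger test than was run. The ranking of the three powers may also partly reflect how the CVBs were obtained.

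**Working it through.** **Inputs.** From the SAP's Sample size section: Group 1 "had a 9-month ED visit rate of 2.22 visits"; Group 2 "had a 9-month ED rate of 1.89 visits"; Group 3 "had a 9-month ED rate of 1.68"; reductions of 72% (active) and 35% (control); 24 schools of 10; alpha .0167; the three CVBs. Assumed, because not stated: 8 schools per arm and a two-sided test.

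**Step 1: are the CVBs compatible?** Let a, b, c be the squared CVBs of arms 1, 2, 3.

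- (a+b)/2 = 0.1331² = 0.01772; (a+c)/2 = 0.1820² = 0.03312; (b+c)/2 = 0.0502² = 0.00252.
- a = 0.01772 + 0.03312 - 0.00252 = 0.0483.
- b = 0.01772 + 0.00252 - 0.03312 = -0.0129, which no variance can equal.
- c = 0.03312 + 0.00252 - 0.01772 = 0.0179.

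Equivalently, with b at least 0, Groups 1 vs 3 cannot exceed √(0.1331² + 0.0502²) = 0.142; the SAP has 0.1820. Weighting arms by 8 or 9 schools leaves b between -0.016 and -0.010.

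**Step 2: power for Groups 2 vs 3.** Follow-up rates are r2 = 1.89 × 0.28 = 0.529 and r3 = 1.68 × 0.65 = 1.092. For a cluster-randomised comparison of two Poisson rates,

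ncp = √8 × |r2 - r3| / √[(r2 + r3)/10 + CVB²(r2² + r3²)].

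At CVB 0.0502 the bracket is 0.1621 + 0.0037 = 0.1658, so ncp = 2.828 × 0.563/0.407 = 3.91. With the normal critical value 2.394, power is 93.5%. Two small-sample corrections bring it down: 7 in place of 8 clusters gives 89.7%, and a noncentral t with 14 degrees of freedom gives 86.5% (88.6% with unrounded reductions). The stated 88% lies inside this span.

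| CVB | t, 14 df | Normal, 7 clusters | Normal, 8 clusters |
|---|---|---|---|
| 0 | 87.4% | 90.4% | 94.1% |
| 0.0502 | 86.5% | 89.7% | 93.5% |
| 0.1331 | 81.4% | 85.1% | 89.9% |
| 0.1820 | 76.2% | 80.2% | 85.8% |
| 0.25 (assumed) | 66.9% | 71.2% | 77.8% |

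Moving from 0.0502 to 0.1331 costs 3.6 to 5.1 points, and to 0.1820 costs 7.7 to 10.3.

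**Step 3: the other two contrasts, same formula.** Group 1's follow-up rate is 2.22 × 0.28 = 0.622.

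- Groups 1 vs 3 at CVB 0.1820: 55.3% (t), 59.4% (7 clusters), 66.3% (8 clusters), against a stated 97%. At CVB 0 it is 69-79%, or at most 83% with unrounded reductions. On this scale Group 1 (0.622) is nearer to control (1.092) than Group 2 (0.529) is, and its CVB is larger, so its power should be below that of Groups 2 vs 3, not above it.
- Groups 1 vs 2 at CVB 0.1331: 4-5%, against a stated 14%.

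A common CVB does not lower every figure: at 0.1331, Groups 1 vs 3 rises from 66.3% to 72.1% (8 clusters).

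**The case against.** **No pooling rule is stated.** If a pair's CVB is the plain average of the arms' CVBs, a solution exists: Group 1 = 0.1331 + 0.1820 - 0.0502 = 0.265, Group 2 = 0.1331 + 0.0502 - 0.1820 = 0.001, Group 3 = 0.1820 + 0.0502 - 0.1331 = 0.099. A reader might infer from Step 1 that the figures are impossible. The documents do not support that, only incompatibility under variance pooling. The alternative still needs almost no variation among Group 2's schools.

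**Noise can produce this.** In simulations with one true CVB of 0.05-0.20 and 8 schools of 10 per arm, pairwise moment estimates implied a negative arm component in about 50-66% of runs. The pattern is therefore not proof of an arithmetic error. If the values are noise, though, 0.0502 has no special claim for one contrast.

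**They may not measure schools at all.** If each figure were the gap between two arm-level values divided by their sum, the first and third would imply (0.1331 + 0.0502)/(1 + 0.1331 × 0.0502) = 0.1821 for Groups 1 vs 3, which matches 0.1820 within rounding of the inputs. The printed baseline rates give 0.080, 0.138 and 0.059 instead, so this origin is unproven. It would make the numbers coherent with one another but wrong as between-school variation.

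**0.0502 is not shown to be implausible, and 88% does not hinge on it.** The documents give no benchmark; the value is small only beside the other two. Setting CVB to 0 adds about 1 point.

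**The effect scale is unknown.** Taking the difference in change from baseline, with Poisson variance from baseline counts only and the CVB applied to follow-up rates (8 clusters, alpha .0167), gives 97.2% and 89.4% for the two control contrasts but 8.7% for Groups 1 vs 2. Close matches to all three figures (14.1%, 97.4%, 87.8%) were found, but they needed alpha .05, the same nonstandard variance and little or no CVB effect. The agreement with 88% in Step 2 may therefore be coincidental. That argues for stating the formula, but it bars calling the 97% wrong on every scale.

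**Conclusion.** The point holds as a defect in the planning figures. Three pair-specific CVBs for one set of schools are unexplained, do not follow from the stated model, and conflict under ordinary variance pooling. On a follow-up-rate comparison, using either of the SAP's other CVBs lowers power for Groups 2 vs 3 by about 4-10 points, to between 76% and 90%. On that basis the 97% and 14% are not reproduced. These sizes rest on an equal split of schools, a two-sided test, the rounded reductions and the follow-up-rate scale.

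A reader might rescale the stated 88% and conclude that about 78% is the true power: 88% implies an ncp of 1.175 + 2.394 = 3.569; times √(0.1658/0.2109) this is 3.165, or about 78% at CVB 0.182. That should not be printed. It rescales a figure whose formula is unknown with one that, without a small-sample correction, gives 93.5%, 66% and 5% where the SAP has 88%, 97% and 14%.

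The primary model, estimate and test are unaffected.

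**What to change.** Estimate one within-arm between-school CVB from all 24 schools, with arm as a fixed effect so that baseline differences between arms do not enter it, and use it for every contrast. State its data source, the power formula, the effect scale (follow-up rate or change), the sidedness and the schools per arm. Recompute and restate all three powers with that formula, and show each over a CVB range such as 0.05-0.25.

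The cost is SAP wording and one re-run on baseline data already held. Some stated powers will become less favourable. No more families are needed.
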